NUMBER OF SUBJECTS: Up to 176 eligible subjects will be randomized (approximately 132 subjects will be assigned to the JUVÉDERM® VOLBELLA® with Lidocaine [hereafter referred to as VOLBELLA with Lidocaine] group and approximately 44 subjects will be assigned to the no-treatment control group).
OBJECTIVES: The objective of this study is to evaluate the safety and effectiveness of VOLBELLA with Lidocaine for lip enhancement in a Chinese population.
STUDY DESIGN: 
This is a prospective, multicenter, randomized, no-treatment-controlled study to evaluate the safety and effectiveness of VOLBELLA with Lidocaine for lip enhancement in a Chinese population.
 
Subjects will be randomized at a 3:1 ratio either to have treatment with VOLBELLA with Lidocaine at the outset of the study (VOLBELLA with Lidocaine group, also referred to as the treatment group) or to have treatment delayed by 3 months (no-treatment control group). Treatment and safety assessments of a subject throughout the study will be performed by the same Treating Investigator (maximum 2 Treating Investigators per site), and effectiveness assessments will be performed by the same Evaluating Investigator. The Evaluating Investigator will remain blinded to treatment assignments throughout the duration of the study. Subjects randomized to the treatment group should undergo treatment on the same day as randomization. If initial treatment does not occur on the randomization day for subjects in the treatment group, it must occur within 30 days after screening. Subjects randomized to the no-treatment control group will attend study visits at months 1 and 3 of the no-treatment control period at which they will undergo effectiveness measures also performed at randomization. These measures include the Evaluating Investigator's assessment of the subject's lip fullness using the 5-point Lip Fullness Scale (LFS; 5 points: Minimal, Mild, Moderate, Marked, and Very Marked) and facial 3-dimensional (3D) imaging. [REDACTED]
 
[REDACTED]
 
[REDACTED] In addition, vital signs will be collected. After the completion of the control period, subjects randomized to the no-treatment control group will receive optional treatment for lip enhancement and follow the same schedule of visits and procedures in the treatment period as described below and in Table 1 for subjects randomized to the treatment group.
 
On the initial treatment day, the trained Treating Investigator will inject VOLBELLA with Lidocaine into the lips, as needed for lip enhancement. Allowable treatment areas are the vermilion body, vermilion border (including the Cupid's bow), and philtral columns. Prior to initial treatment, the Evaluating Investigator and the subject will rate the subject's lip fullness by using the LFS, and the Evaluating Investigator will rate the subject's philtral column definition by using a 5-point scale (Not Defined, Barely Defined, Somewhat Defined, Well-defined, and Very Well-defined). On day 30 after initial treatment, the Evaluating Investigator will again rate the subject's lip fullness and philtral column definition. Subjects may undergo an optional touch-up treatment at the day 30 visit after initial treatment, if the Treating Investigator assesses that optimal correction was not achieved. At each treatment visit, the subject will rate procedural pain on an 11-point scale immediately after receiving the injections, and the Treating Investigator will assess the ease of injection and the product moldability. Subjects will complete a safety diary for 30 days after each treatment and will complete a safety follow-up telephone call at 3 days after each treatment. Before treatment on each treatment day, the subject will undergo facial 3D imaging, which will also be performed 30 days after treatment.
 
Routine follow-up visits for safety and effectiveness will occur at 1, 3, and 6 months after the last treatment for both groups. At these visits, facial 3D imaging will be performed, [REDACTED]


Approval Date: 29-Jul-2015

[REDACTED]

Long-term safety data will be collected by telephone call at 9 months after the last treatment for the control group and at 9 and 12 months after the last treatment for the treatment group. Throughout the study, the Treating Investigator (or designee) will monitor the subjects for safety.

DIAGNOSIS AND CRITERIA FOR INCLUSION/EXCLUSION: Chinese adults seeking lip enhancement

INCLUSION:

1. male or female, 18 years of age or older
2. has an overall baseline score of Minimal, Mild, or Moderate on the 5-point LFS, as assessed by the Evaluating Investigator, and desires to achieve at least a 1-point improvement in overall LFS score after treatment

[REDACTED]

4. has the ability to follow study instructions and is likely to complete all required visits

[REDACTED]

EXCLUSION:

1. has lip tattoos, piercings, facial hair, or scars that would interfere with visualization of the lips and perioral area for the effectiveness assessments

[REDACTED]

[REDACTED]

[REDACTED]

[REDACTED]

[REDACTED]

[REDACTED]

[REDACTED]

[REDACTED]

10. is on an ongoing regimen of anti-coagulation therapy (eg, warfarin)

[REDACTED]

Approval Date: 29-Jul-2015

[REDACTED]

14. has current cutaneous inflammatory or infectious processes (eg, acne or herpes), an abscess, an unhealed wound, or a cancerous or precancerous lesion in the mouth area (study treatment may be delayed so that subjects with a history of recurrent oral herpes can take prophylactic antiviral/herpes medication for 2 days)

[REDACTED]

TEST PRODUCT, DEVICE VOLUME, AND MODE OF ADMINISTRATION:
VOLBELLA with Lidocaine hyaluronic acid dermal filler will be injected into the lips and, if needed, the philtral columns using a 30 G x 1/2-inch needle. The appropriate injection volume will be determined by the Treating Investigator but is not to exceed a maximum total of 4.0 mL for initial and touch-up treatments combined.

DURATION OF STUDY: treatment period: 1 to 30 days; follow-up period: up to 12 months

RESPONSE MEASURES:
Effectiveness: The primary effectiveness measure is the Evaluating Investigator's assessment of overall lip fullness using the 5-point LFS. The secondary effectiveness measures are the subject's assessment of overall lip fullness using the 5-point LFS, the volume of the overall lips measured from 3D images, and the lip surface area change measured from 3D images. [REDACTED]

Safety: Safety will be evaluated by subject assessment of procedural pain; by the severity and duration of injection site responses (ISRs), which will be reported in the subject safety diary for 30 days after each treatment; and by any reported adverse events at all follow-up visits throughout the study.

STATISTICAL METHODS:
Sample Size Calculation: A sample size of 111 randomized subjects treated with VOLBELLA with Lidocaine and 37 randomized untreated control subjects will provide > 96% power to detect the superiority of

Approval Date: 29-Jul-2015

VOLBELLA with Lidocaine over no treatment for responder rate at month 3. Responder rate is the percentage of subjects who show at least a 1-point improvement compared with baseline on the 5-point LFS based on the Evaluating Investigator's assessment of overall lip fullness. A 2-sided Fisher's Exact test with 5% significance level will be used to calculate the power, assuming responder rates of 79.0% for the VOLBELLA with Lidocaine group and up to 44.1% for the no-treatment control group at month 3. The assumed responder rates are based on the results of a US study of JUVÉDERM® Ultra XC for the lips (Study JULIDO-002). The power calculation was performed using an Inequality Test for 2 Independent Proportion [Difference] in PASS software (Version 2008). The planned sample size is considered to be adequate for evaluation of long-term (ie, 12-month) safety.

Approximately 15% of subjects may drop out after receiving treatment or not provide data at month 3. To accommodate this, 176 subjects will be randomized, with at least 132 subjects assigned to the VOLBELLA with Lidocaine group and approximately 44 subjects assigned to the no-treatment control group.

Effectiveness: The primary effectiveness variable is lip response based on the Evaluating Investigator's assessment of overall lip fullness using the 5-point LFS. A subject showing ≥ 1 -point improvement (increase in fullness) compared with baseline will be considered to be a lip responder. The primary evaluation timepoint is month 3 after last treatment for subjects in the VOLBELLA with Lidocaine group and month 3 after randomization for subjects in the no-treatment control group.

The primary effectiveness analysis will test for superiority of VOLBELLA with Lidocaine over no treatment in the difference in overall lip fullness responder rate. Two-sided Fisher's exact test with 5% significance level will be used to compare treatment effects between VOLBELLA with Lidocaine group and the no-treatment control group. If the 2-sided p-value is less than 0.05 and the responder rate is greater for the VOLBELLA with Lidocaine group than for the no-treatment control group, then VOLBELLA with Lidocaine will be considered superior to no-treatment.

Secondary effectiveness analyses will include 1) responder rate and the corresponding 2-sided 95% exact CI based on the subject's assessment of overall lip fullness at month 3 for the treatment group, 2) change from baseline to month 3 in volume of the overall lips, and 3) the percentage change from baseline to month 3 in lip surface area using t-test or Wilcoxon rank-sum test, as appropriate.

All effectiveness analyses will be performed on the modified intent-to-treat (mITT) population, defined as all subjects who are randomized to study treatment (treatment group), receive at least 1 study device treatment, and have baseline and at least 1 posttreatment assessment of the primary variable, and subjects who are randomized to the no-treatment control group and have baseline and at least 1 follow-up assessment of the primary variable. Additional sensitivity analyses for the primary effectiveness variable will be performed on the per-protocol (PP) population, defined as all mITT subjects who do not have any significant protocol deviations that affect the primary effectiveness endpoint. All analyses will be performed without data imputation.

Safety: Procedural pain will be summarized using descriptive statistics. ISRs reported in subject diaries will be summarized by treatment (initial and touch-up), symptom, maximum reported severity, and maximum reported duration. Summaries will include the incidence rate for each ISR.

Adverse events will be summarized by System Organ Class and Preferred Term and will be tabulated by duration, severity, causality, action taken, relationship to treatment, and outcome. The summary will include incidence rate as well as total number of events.

Table of Contents

Synopsis	3
Table of Contents	7
List of Tables.....	10
1. Abbreviations and Terms	17
2. Background, Risk and Benefit, and Clinical Rationale	18
2.1 Background	18
2.2 Risk and Benefit.....	20

2.1 Background

Lip augmentation to restore fullness and definition loss due to hypoplasia or aging has become a common use for hyaluronic acid (HA) dermal fillers ([Eccleston and Murphy, 2012](#); [Philipp-Dormston et al, 2014](#)). Treatment with temporary HA fillers can provide volume to the lips and perioral area, restoring fullness and the natural contour of the region to which it is applied.

JUVÉDERM® VOLBELLA® with Lidocaine (hereafter referred to as VOLBELLA with Lidocaine), CE-marked in 2011 and included in the JUVÉDERM range of products, is a malleable gel that meets the physical constraints that would be experienced with injection and volume expansion of the lips. VOLBELLA with Lidocaine is formulated using a combination of high and low molecular weight HA, which reduces the concentration of crosslinking reagent needed while increasing overall crosslinking efficiency. The final formulation includes a small quantity of noncross-linked HA to decrease extrusion force during injection, and lidocaine (0.3% w/w) to increase patient comfort. In a postmarketing study, JUVÉDERM VOLBELLA without Lidocaine (received European marking of conformity [CE mark] in 2007) was demonstrated to be safe and effective in providing smooth and natural improvement in lip fullness ([Eccleston and Murphy, 2012](#)). VOLBELLA with Lidocaine represents an improvement with the addition of 0.3% (w/w) lidocaine hydrochloride to reduce procedural pain.

In Europe and other countries, numerous fillers have been used in the lips and perioral area. In the US, Restylane® and Restylane-L® (with lidocaine) are the only dermal fillers currently approved for lip augmentation. In China, no dermal fillers are approved for lip augmentation. As described below, investigations assessing the safety and effectiveness of HA-based dermal fillers for volume restoration of the lips have demonstrated treatment success and high patient satisfaction.

- In a multicenter European postmarket study of the safety and effectiveness of JUVÉDERM VOLBELLA without Lidocaine, 60 subjects desiring lip enhancement were treated. The filler was injected into the upper and lower lips, perioral lines, and oral commissures. Three months after treatment, 93.2% of subjects displayed ≥ 1 point improvement on the 4-point Lip Fullness Scale (LFS). After treatment, 84.0% of subjects displayed ≥ 1 -point improvement on the 4-point Perioral Lines Severity Scale

and 70.0% displayed ≥ 1 -point improvement on the 4-point Oral Commissures Severity Scale. At the end of the study (12 months), 94.1% of subjects were satisfied with the overall effects of the treatment ([Eccleston and Murphy, 2012](#)).

- In the pivotal study evaluating the safety and effectiveness of Restylane for soft tissue augmentation of the lips, 92.6% of 134 treated subjects displayed ≥ 1 -point improvement 8 weeks after treatment on the 5-point Medicis LFS compared with baseline assessment, and 90.1% of subjects displayed ≥ 1 -point improvement 12 weeks after treatment (Restylane Directions for Use, 2011).
- In a multicenter, feasibility study of lip enhancement conducted in the United States (US), 50 subjects were injected with JUVÉDERM Ultra in the upper and lower lips, perioral lines, and oral commissures. At 12 weeks after treatment, 71% of subjects improved by ≥ 1 point on the 4-point LFS, 51% of subjects improved by ≥ 1 point on the Perioral Lines Severity Scale, and 64% of subjects improved by ≥ 1 point on the Oral Commissures Severity Scale (all of which were evaluated by a blinded Evaluating Investigator). Overall subject satisfaction at 12 weeks was 82% ([Fagien et al, 2013](#)).
- In a large, non-randomized study, 1,446 subjects were treated with Restylane for lip augmentation and visible facial rhytides (2,242 treated areas). Subject satisfaction was 77.8% at 3 months, declining to 36.4% at 9 months. The filling effect lasted longer in areas that were not subjected to animation (eg, glabellar lines), which was reflected in subject satisfaction trends ([Bosniak et al, 2004](#)).
- Sixty-six subjects were treated with Restylane for lip augmentation in specific lip zones to allow for targeted volume enhancement in which the gel could easily be injected with a 30 G needle. Mean satisfaction on a scale of 0 to 5 (5 being most satisfied) was 4.5. Mean persistence until lips returned to preoperative appearance was 4.9 months. No adverse events were observed ([Jacono, 2008](#)).
- In an open-label pilot study assessing the effectiveness of Restylane for restoring lip fullness, lip volume changes were measured in 21 subjects at several timepoints through 12 weeks after treatment. At 12 weeks after treatment, 79% of subjects had ≥ 1 -point improvement on a 5-point lip fullness scale, as rated by an independent evaluator ([Solish and Swift, 2011](#)).

- A postmarketing surveillance study assessed treatment comfort and aesthetic effect in 57 patients treated with JUVÉDERM Ultra Smile. The most common site for injection was the vermilion border, and 95% of injectors found the gel easy to inject. Furthermore, 99% of injectors rated an improved aesthetic compared to baseline. Patient satisfaction with the product was 96% (Lanigan, 2011).

As with any dermal filler injection, pain during administration is a possible side effect and may compromise the physician's ability to inject precisely (Segall and Ellis, 2007). Physicians typically use pain-relieving agents concomitant with injection, such as a nerve block, topical anesthetic, or a local anesthetic. The inclusion of lidocaine in HA dermal fillers is intended to reduce the patient's pain during the procedure and reduce or eliminate the need for additional pain-relieving agents. Ninety-three percent of subjects, randomized to treatment with JUVÉDERM Ultra or Ultra Plus in 1 nasolabial fold and JUVÉDERM Ultra or Ultra Plus including 0.3% lidocaine in the other nasolabial fold, rated the lidocaine formulations less or slightly less painful than the JUVÉDERM Ultra or Ultra Plus (Weinkle et al, 2009). As reviewed by Smith and Cockerham (2011), additional studies have demonstrated significantly less pain associated with dermal fillers containing lidocaine, allowing for a quick treatment, reduced recovery time, and high patient satisfaction. Furthermore, lidocaine in HA fillers has been shown not to affect the rheology, duration of effect, or frequency of adverse events (Andre, 2008; Gold, 2009; Raspaldo et al, 2010; Rivkin, 2009).

2.2 Risk and Benefit

A risk analysis linked to the manufacturing, biocompatibility, and use of VOLBELLA with Lidocaine was conducted according to International Organization for Standardization (ISO) 14971:2007 and is detailed in the risk management file. An overview of these risks and additional risks related to the injection procedure is contained within the Investigational Plan Risk Analysis. Each device contains 15 mg HA of nonanimal origin cross-linked with a minimal amount of 1,4-butanediol diglycidyl ether (BDDE), 3 mg lidocaine hydrochloride, and 1 mL QS phosphate buffer pH 7.2 supplied in a syringe composed of cyclic olefin copolymer. Assessment of overall risks that could have a high severity of consequences revealed that preventative actions guaranteed residual risks graded "very low," "low," or "moderate," with no risk graded as "unacceptable."

However, as with any skin or lip injection, risks exist with the injection procedure itself, the anesthetic agent, and the type of injection (in this case an HA facial injection). Risks related to the injection procedure and/or the device include redness, pain, tenderness, swelling,

itching, firmness, lumps and bumps, and delayed adverse reactions. These risks are common to all dermal filler injection procedures. Risks associated with the anesthetic agent include allergic reactions that may manifest as an anaphylactic reaction, skin rash, redness, itching, hives, burning, stinging, swelling, tenderness, and transient loss of skin color. The use of a small-gauge needle to deliver the experimental device used in this clinical study is intended to minimize tissue trauma. The inclusion of 0.3% lidocaine in VOLBELLA with Lidocaine is meant to reduce pain during the injection and during the hours following injection as well as to provide consistency in anesthetic dosing. It is advisable to take the potential risks into account. Furthermore, the literature analysis and medical device reporting from US Food and Drug Administration (FDA) approved dermal filler products reveal that pre-existing pathological conditions of patients along with the contraindications and precautions for use as written in the investigational directions for use (IDFU) should be carefully reviewed.

The benefit of using HA dermal fillers for lip enhancement has been demonstrated by the published literature showing the safety and effectiveness of treatment and by studies of JUVÉDERM products for equivalent indications. Characteristics of VOLBELLA with Lidocaine potentially increase the benefit of use of HA dermal fillers for lip enhancement.

2.3 Clinical Rationale

Although various materials have been investigated as potential candidate soft-tissue fillers, none have produced as consistent and optimal lip enhancement as HA dermal fillers. HA can enhance lip volume ([Sarnoff et al, 2012](#)). The safety and effectiveness of VOLBELLA (without lidocaine) for lip enhancement has been demonstrated in European subjects ([Eccleston and Murphy, 2012](#)). However, European and Chinese ideals of beautiful lips differ; consequently, the use of dermal fillers and their safety and effectiveness for lip enhancement may differ.

Risks associated with VOLBELLA with Lidocaine have been mitigated by the product's formulation, and potential complications that may arise have been described in the literature and IDFU. Therefore, VOLBELLA with Lidocaine is expected to be safe and effective. Study VOLBELLA-005 is intended to provide safety and effectiveness data on VOLBELLA with Lidocaine for lip enhancement to support a Chinese Food and Drug Administration (CFDA) pre-market application.

3. Study Objectives and Clinical Hypotheses

3.1 Study Objectives

The objective of this study is to evaluate the safety and effectiveness of VOLBELLA with Lidocaine for lip enhancement in a Chinese population.

3.2 Clinical Hypotheses

The percentage of subjects with a clinically significant change in lip fullness from baseline to month 3 will be significantly greater in subjects treated with VOLBELLA with Lidocaine than in untreated control subjects.

4. Study Design

4.1 Structure

This is a prospective, multicenter, randomized, no-treatment-controlled study. Up to 9 investigational sites will enroll and follow subjects who meet the study criteria.

4.2 Duration

The study will span a total of approximately 22 months including an estimated 8 months for recruitment, up to 30 days between screening and randomization, up to 1 month for treatment, and up to 12 months for follow-up. Participation for subjects randomized to the treatment group will encompass up to 1 month for treatment and 12 months of follow-up. Participation for subjects randomized to the no-treatment control group will encompass a 3-month no-treatment period, up to 1 month for optional treatment, and 9 months of follow-up.

4.3 Treatment Groups and Treatment Regimen

4.3.1 Study Treatment

VOLBELLA with Lidocaine injectable gel

4.3.2 Control Treatments

A no-treatment control group is included.

4.3.3 Methods for Blinding

The Evaluating Investigator will remain blinded to treatment assignments throughout the duration of the study. The Evaluating Investigator will not be present during the injection procedures.

The Treating Investigator will not discuss the randomized treatment assignments with or in the presence of the Evaluating Investigator.

The Treating Investigators, study coordinators, and subjects will not be blinded to treatment, but they will secure the randomization and other records (eg, records of study treatments and prior study assessments) from potential discovery by the Evaluating Investigator.

The device accountability log will include the kit numbers. The Evaluating Investigator will not have access to the device accountability log.

4.3.4 Retreatment Criteria

One month (30 days) after the initial treatment, the subject and Treating Investigator will discuss the results of the initial treatment and determine whether optimal correction has been achieved. If optimal correction has not been achieved, the Treating Investigator may perform a touch-up treatment. Moreover, if the Evaluating Investigator has determined that the subject's LFS score has not improved by at least 1 point, the subject should receive a touch-up injection.

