### **4.1 Study Design Summary**

#### **4.1.1 Overall Design**

This is a randomized, multicenter, no-treatment-controlled study of the safety and effectiveness of JUVÉDERM® VOLBELLA® with Lidocaine for lip enhancement in Chinese adults. Subjects will be randomized at a 3:1 ratio either to have treatment with VOLBELLA with Lidocaine at the outset of the study (VOLBELLA with Lidocaine group, also referred to as the treatment group, or VOLBELLA group) or to have treatment delayed by 3 months (no-treatment control group, also referred to as the control group). Subjects with Lip Fullness Scale (LFS) score of Minimal, Mild, or Moderate as assessed by Evaluating Investigator (EI) will be enrolled in the study based on inclusion criteria. Randomization will be stratified by baseline LFS score (ie, LFS score rated as Minimal, Mild, or Moderate at the randomization visit by EI).

Treatment and safety assessments of a subject throughout the study will be performed by the same Treating Investigator(TI) (maximum 2 TIs per site), and effectiveness assessments will be performed by the same EI. The EI will remain blinded to treatment assignments throughout the duration of the study.

For subjects randomized to the treatment group, the study treatment will be on the same day as randomization (or within 30 days after screening). Subjects may undergo an optional touch-up treatment at the day 30 visit after initial treatment, if the TI assesses that optimal correction was not achieved. Routine follow-up visits for safety and effectiveness will occur at 1, 3, and 6 months after the last treatment (initial or touch-up treatment, whichever is last). Long-term safety data will be collected by telephone call at 9 and 12 months after the last treatment.

Meanwhile, subjects randomized to the no-treatment control group will attend study visits at months 1 and 3 of the no-treatment control period. After the completion of the control period, control group will receive optional treatment and optional touch-up treatment. Routine follow-up visits will occur at 1, 3, and 6 months. Safety follow-up phone call will be at 9 months.

At initial treatment visit, the TI will inject the treatment into the vermilion body, vermilion border (including the Cupid's bow), and philtral columns, as needed for lip enhancement. The

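### Section 4.3.4 credits the blinded Evaluating Investigator with judging LFS improvement and ties a touch-up to it, at odds with the blinding rule and with the touch-up wording in the synopsis and SAP

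*Protocol*

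**What the plan says.** - **Touch-up, Protocol 4.3.4.** There are two criteria. The first rests with the Treating Investigator after discussion with the subject: "If optimal correction has not been achieved, the Treating Investigator may perform a touch-up treatment". The second is added to it, as a condition: "Evaluating Investigator has determined that the subject's LFS score has not improved by at least 1 point, the subject should receive a touch-up injection".
- **Touch-up, Protocol synopsis (Study Design).** Subjects may have "an optional touch-up treatment at the day 30 visit after initial treatment, if the Treating Investigator assesses that optimal correction was not achieved". At that visit the Evaluating Investigator's task is to rate: "On day 30 after initial treatment, the Evaluating Investigator will again rate the subject's lip fullness and philtral column definition".
- **Touch-up, SAP 4.1.1.** The touch-up is again optional, "if the TI assesses that optimal correction was not achieved".
- **Blinding, Protocol 4.3.3.** "The Evaluating Investigator will remain blinded to treatment assignments throughout the duration of the study". Treating Investigators, coordinators and subjects are open, and must secure the randomization and other records, giving as examples "records of study treatments and prior study assessments) from potential discovery by the Evaluating Investigator".
- **Rater and endpoint.** One Evaluating Investigator makes all of a subject's effectiveness assessments (synopsis). The primary variable is that person's finding of at least a 1-point LFS gain at month 3 (Protocol 8.2.1).

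**The concern.** Subjects and Treating Investigators know the allocation, so the primary endpoint depends on the Evaluating Investigator's blind. The endpoint is a one-grade change on a five-grade visual scale. Protocol 8.5 allows for up to 44.1% of untreated controls meeting it, so the plan does not treat one-grade changes without treatment as rare.

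Two things are at stake. First, 4.3.4 as worded gives the blinded rater a comparison that 4.3.3 is meant to prevent, with a consequence that arises in only one arm before month 3. Second, sites can read different rules on when a touch-up is given. A touch-up is part of the treatment course and restarts the clock for the primary visit, since month 3 runs from the last treatment.

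**Working it through.** No figure in the plan is in dispute, so the check is mainly a side-by-side reading.

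**1. Touch-up criteria**

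| Place | Who assesses | On what | Force |
|---|---|---|---|
| Protocol synopsis | Treating Investigator | optimal correction | optional |
| Protocol 4.3.4, first criterion | Treating Investigator, with subject | optimal correction | may |
| Protocol 4.3.4, second criterion | Evaluating Investigator | LFS gain below 1 point | should |
| SAP 4.1.1 | Treating Investigator | optimal correction | optional |

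The rows diverge when the Treating Investigator is satisfied but the Evaluating Investigator's grade has not risen. The third row then calls for a touch-up and the others do not.

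**2. Does the determination need the earlier score?** Entry requires a baseline of Minimal, Mild or Moderate (Protocol 5.3), which is 0, 1 or 2 on Protocol Table 4. Taking each possible day 30 grade:
- Grade 0: a gain of 1 or more is impossible, so baseline is not needed.
- Grade 1: a gain only if baseline was 0, so baseline is needed.
- Grade 2: a gain only if baseline was 0 or 1, so baseline is needed.
- Grade 3 or 4: a gain whatever the baseline, so baseline is not needed.

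For grades 1 and 2, the rater cannot make the determination without the score that 4.3.3 keeps back. Both instructions cannot be followed to the letter.

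**3. Can it reveal allocation?** Controls attend at months 1 and 3 and are rated on the LFS, with no treatment until the control period ends. Their month 1 target is Day 31, counting randomization as Day 1 (SAP Tables 6-1 and 6-3). That is 31 − 1 = 30 days after randomization, close to the day 30 rating in the VOLBELLA arm. The rating is therefore common to both arms. What differs is the touch-up decision, which before the primary timepoint exists only for treated subjects. The route opens if the rater compares with baseline for that purpose, or knows what the comparison leads to.

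**4. Timing.** The month 3 target is Day 91, with Day 1 the last treatment (SAP Tables 6-1 and 6-2), so 90 days after it. With a touch-up on day 30, the primary rating falls about 90 days (3 months) after the day 30 rating. Without one it falls 90 − 30 = 60 days (2 months) after.

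**5. Sample size.** Enumerating the two-sided 5% Fisher's exact test for 111 and 37 subjects at 79.0% and 44.1% gives 96.7% power, which reproduces the stated figure of more than 96%. Rewording 4.3.3 and 4.3.4 alters none of these inputs.

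**The case against.** The strongest reply is that 4.3.4 is loose wording for a sound process. The LFS is an absolute scale with fixed descriptors, so the Evaluating Investigator can grade without baseline. Unblinded staff hold the earlier scores and can do the subtraction. The synopsis has this investigator only rate at day 30, and the Treating Investigator gives the injection. Section 4.3.3 already withholds treatment records and the device log and keeps the rater out of the injections. The visit-by-visit procedures in Section 6 are redacted and may describe such a hand-off. A synopsis and a SAP design summary may also be shorter than the operative section.

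Much of this stands. It makes a workable reading likely and rules out saying that a hand-off is missing from the plan. It does not change the visible text of 4.3.4, which credits the comparison to the blinded rater, or the gap between *should* there and *optional* elsewhere.

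Four stronger readings are tempting, and the documents do not support them:
- *The blinded rater decides on retreatment.* This investigator's finding is one of two criteria, and the Treating Investigator performs the touch-up.
- *Following 4.3.4 tells the rater who was treated.* Controls are also rated at month 1, so the day 30 rating alone need not reveal allocation.
- *The bias can be put at about 6 to 16 points.* Assume that knowing allocation reverses 10–25% of calls among the 21% VOLBELLA non-responders (2.1–5.3 points) and the 44.1% control responders (4.4–11.0 points). The sum is 6.5–16.3 of the planned 79.0 − 44.1 = 34.9 points. The reversal share has no source in the documents, and the sum treats every subject as unblinded through this one clause.
- *The comparison always comes about 3 months before the primary rating.* That holds only for touched-up subjects.

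**Conclusion.** The point holds as an inconsistency with a possible effect on the blind. On its literal wording, 4.3.4 conflicts with 4.3.3. Its second touch-up criterion also differs from the synopsis and SAP 4.1.1 in both assessor and force. Allocation could be inferred before the primary rating if the Evaluating Investigator makes the comparison or knows its consequence. Whether either happens at sites cannot be told from the documents, and any effect on the responder rates cannot be estimated from them.

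This rests on the visible text; the redacted procedures may already settle who compares the scores. The change is worth making because it is cheap and protects the one blinded assessor of the primary endpoint. One limit remains: a touch-up restarts the visit schedule, so a touched-up subject may have an extra rating visit before month 3 that controls do not have. That follows from the schedule whoever triggers the touch-up.

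**What to change.** State in Protocol 4.3.3 and 4.3.4 that:
- the Evaluating Investigator records only the current absolute LFS grade, on the same form in both arms, without access to earlier scores;
- the change from baseline is derived by the eCRF or by unblinded staff and passed only to the Treating Investigator;
- the Evaluating Investigator is not told whether a touch-up follows.

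Reconcile the touch-up wording in the synopsis, Protocol 4.3.4 and SAP 4.1.1 so that all three state the same criterion with the same force. Which criterion that is remains for the sponsor to decide.

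The cost is protocol and form wording, plus one derived field for unblinded staff to handle at day 30. No visit, rater or procedure is added.
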